7.2.2 Reporting of Pregnancy and Lactation to the Sponsor

Although pregnancy and lactation are not considered adverse events, it is the responsibility of investigators or their designees to report any pregnancy or lactation in a subject (spontaneously reported to them) that occurs during the trial.

Pregnancies and lactations that occur after the consent form is signed but before treatment allocation/randomization must be reported by the investigator if they cause the subject to be excluded from the trial, or are the result of a protocol-specified intervention, including but not limited to washout or discontinuation of usual therapy, diet, placebo treatment or a procedure. Pregnancies and lactations that occur from the time of treatment allocation/randomization through 120 days following cessation of Sponsor's product, or 30 days following cessation of treatment if the subject initiates new anticancer therapy, whichever is earlier, must be reported by the investigator. All reported pregnancies must be followed to the completion/termination of the pregnancy. Pregnancy outcomes of spontaneous abortion, missed abortion, benign hydatidiform mole, blighted ovum, fetal death, intrauterine death, miscarriage and stillbirth must be reported as serious events (Important Medical Events). If the pregnancy continues to term, the outcome (health of infant) must also be reported.

Such events must be reported within 24 hours to the Sponsor either by electronic media or paper. Electronic reporting procedures can be found in the EDC data entry guidelines. Paper reporting procedures can be found in the Investigator Trial File Binder (or equivalent).

7.2.3 Immediate Reporting of Adverse Events to the Sponsor

7.2.3.1 Serious Adverse Events

An serious adverse event is any adverse event occurring at any dose or during any use of Sponsor's product that:

- Results in death;
- Is life threatening;
- Results in persistent or significant disability/incapacity;
- Results in or prolongs an existing inpatient hospitalization;
- Is a congenital anomaly/birth defect;
- Is an other important medical event.

Note: In addition to the above criteria, adverse events meeting either of the below criteria, although not serious per ICH definition, are reportable to the Sponsor in the same timeframe

MK-3475-394-06 Final Protocol 03-Nov-2022 Confidential

Protocol/Amendment No.: 394-06

as SAEs to meet certain local requirements. Therefore, these events are considered serious by the Sponsor for collection purposes.

• Is a new cancer (that is not a condition of the study);

• Is associated with an overdose.

Refer to Table 7 for additional details regarding each of the above criteria.

For the time period beginning when the consent form is signed until treatment allocation/randomization, any serious adverse event, or follow up to a serious adverse event, including death due to any cause other than progression of the cancer under study (refer to [Section 7.2.3.3] for additional details), that occurs to any subject must be reported within 24 hours to the Sponsor if it causes the subject to be excluded from the trial, or is the result of a protocol-specified intervention, including but not limited to washout or discontinuation of usual therapy, diet, placebo treatment or a procedure.

For the time period beginning at treatment randomization through 90 days following cessation of trial treatment, or 30 days following cessation of trial treatment if the subject initiates new anticancer therapy, whichever is earlier, any serious adverse event, or follow up to a serious adverse event, including death due to any cause, other than progression of the cancer under study (reference Section 7.2.3.3 for additional details) whether or not related to the Sponsor's product, must be reported within 24 hours to the Sponsor either by electronic media or paper. Electronic reporting procedures can be found in the EDC data entry guidelines. Paper reporting procedures can be found in the Investigator Trial File Binder (or equivalent).

Additionally, any serious adverse event, considered by an investigator who is a qualified physician to be related to the Sponsor's product that is brought to the attention of the investigator at any time following consent through the end of the specified safety follow-up period specified in the paragraph above, or at any time outside of the time period specified in the previous paragraph also must be reported immediately to the Sponsor.

All subjects with serious adverse events must be followed up for outcome.

7.2.3.2 Events of Clinical Interest.

Selected non-serious and serious adverse events are also known as Events of Clinical Interest (ECI) and must be reported to the Sponsor.

For the time period beginning when the consent form is signed until treatment allocation/randomization, any ECI, or follow up to an ECI, that occurs to any subject must be reported within 24 hours to the Sponsor if it causes the subject to be excluded from the trial, or is the result of a protocol-specified intervention, including but not limited to washout or discontinuation of usual therapy, diet, placebo treatment or a procedure.

For the time period beginning at treatment allocation/randomization through 14 days following cessation of treatment, any ECI, or follow up to an ECI, whether or not related to

MK-3475-394-06 Final Protocol 03-Nov-2022 Confidential

Protocol/Amendment No.: 394-06

the Sponsor's product, must be reported within 24 hours to the Sponsor, either by electronic media or paper. Electronic reporting procedures can be found in the EDC data entry guidelines. Paper reporting procedures can be found in the Investigator Trial File Binder (or equivalent).

Events of clinical interest for this trial include:

- 1) An overdose of Sponsor's product, as defined in Section 7.2.1 Definition of an Overdose for This Protocol and Reporting of Overdose to the Sponsor, that is not associated with clinical symptoms or abnormal laboratory results.
- 2) Hepatic ECIs include any of the following events. All of these events will require holding study treatment, notification of the event(s) to the Sponsor within 24 hours via electronic media or paper, and a hepatology consultation if necessary. For dose interval modification, refer to Section 5.2.1.2. For guidance related to the diagnosis and management of hepatic ECIs, refer to Section 5.2.1.3.

a. ALT:

- i. Among subjects with baseline ALT $<2\times$ ULN: ALT $\ge 5\times$ ULN
- ii. Among subjects with baseline ALT $\ge 2 \times ULN$: ALT $> 3 \times$ the baseline level
- iii. ALT >500 U/L regardless of baseline level

b. AST:

- i. Among subjects with baseline AST $\leq 2 \times ULN$: AST $\geq 5 \times ULN$
- ii. Among subjects with baseline AST $\ge 2 \times ULN$: AST $> 3 \times$ the baseline level
- iii. AST >500 U/L regardless of baseline level

c. Total Bilirubin:

- i. Among subjects with baseline levels <1.5 mg/dL: a value of >2.0 mg/dL
- ii. Among subjects with baseline levels that are ≥ 1.5 mg/dL: a value $\ge 2 \times$ the baseline level
- iii. Total bilirubin >3.0 mg/dL regardless of baseline level

Protocol/Amendment No.: 394-06

d. Regardless of laboratory values, hepatic decompensation diagnosed clinically, including:

- i. New onset clinically detectable ascites
- ii. Gastrointestinal bleeding suggestive of portal hypertension (e.g., esophageal or gastric varices)
- iii. Hepatic Encephalopathy

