5.2.1.3 Guidance for Diagnosis and Management of Hepatic Events of Clinical Interest

In addition to overdose, hepatic ECIs will include any of the following events. All of these events will require holding study treatment, notification of the Sponsor within 24 hours, and a hepatologist consultation (if necessary). All cases of retreatment and permanent discontinuation must be reported to the Sponsor and recorded in the database. Refer to Section 7.2.3.2 for reporting guidelines and the definition of hepatic ECIs.

a. ALT:

- i. Among subjects with baseline ALT $<2\times$ ULN: ALT $\ge 5\times$ ULN
- ii. Among subjects with baseline ALT $\ge 2 \times ULN$: ALT $> 3 \times$ the baseline level
- iii. ALT >500 U/L regardless of baseline level

Protocol/Amendment No.: 394-06

b. AST:

- i. Among subjects with baseline AST $\leq 2 \times ULN$: AST $\geq 5 \times ULN$
- ii. Among subjects with baseline AST ≥2×ULN: AST >3× the baseline level
- iii. AST >500 U/L regardless of baseline level
- c. Total Bilirubin:
 - i. Among subjects with baseline levels <1.5 mg/dL: a value of >2.0 mg/dL
 - ii. Among subjects with baseline levels that are ≥ 1.5 mg/dL: a value $\ge 2 \times$ the baseline level
 - iii. Total bilirubin >3.0 mg/dL regardless of baseline level
- d. Regardless of laboratory values, hepatic decompensation diagnosed clinically, including:
 - i. New onset clinically detectable ascites
 - ii. Gastrointestinal bleeding suggestive of portal hypertension (e.g., esophageal or gastric varices)
 - iii. Encephalopathy

Immediate assessment

All subjects

- All subjects should be evaluated according to directions below within 72 hours of alert for non-overdose hepatic ECI
- Procedures:
 - Obtain a consultation with a hepatologist (if necessary)
 - Obtain a work-up for hepatitis if there is no underlying hepatitis, including hepatitis A, B,C, D, E, Epstein-Barr virus, and cytomegalovirus
 - Assess for ingestion of drugs/supplements with hepatotoxic potential
 - Assess for alcohol ingestion
 - Assess for potential bacterial infection, biliary obstruction, or occult gastrointestinal bleeding

Product: MK-3475 44

Protocol/Amendment No.: 394-06

• Repeat ALT, AST, T-bil, D-bil, ALP, γ-glutamyl transpeptidase, INR, and complete blood count (CBC) with differential

- o Other laboratories or imaging studies as clinically indicated
- Consider liver biopsy if indicated by hepatologist

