- c. SAEs will be followed through 90 days following cessation of treatment, or 30 days following cessation of treatment if the subject initiates new anticancer therapy, whichever is earlier. All protocol specific hepatic ECIs will be collected throughout the study as listed in Section 7.2.3.2. If any of the hepatic ECI criteria are met, collect the Child-Pugh score until the hepatic ECIs resolve.
- d. If any of the hepatic ECI criteria are met, document the Child Pugh score with each visit until the hepatic ECIs resolve.
- e. ECOG Performance Status, Child-Pugh Score, and laboratory tests for screening and determining eligibility are to be performed within 7 days prior to the first dose of trial treatment except hepatitis and thyroid tests, which may be performed within 28 days.
- f. See Section 4.2.3.3 for details regarding administration of Patient Reported Outcomes (PROs). All PROs are to be performed at Cycle 1, Cycle 2, Cycle 3, Cycle 4, Cycle 5 and Cycle 7. After Cycle 7 (Week 18), PROs are to be performed every 9 weeks (e.g., Week 27, Week 36, Week 45). PROs are to be performed up to a year or End of Treatment, whichever comes first, at treatment discontinuation, and at the 30-day post-treatment discontinuation follow-up visit. A visit window of ±7 days will apply to PRO visit assessment. See Section 7.1.2.7 for timing and order of PROs at each visit.
- For women of reproductive potential, a urine or serum pregnancy test should be performed within 72 hours prior to receiving the first dose of study medication (Cycle 1 Day 1). A serum test can be done if urine is not appropriate. Additionally, if urine test is positive or is not evaluable, a serum test is required. Subjects must be excluded/discontinued in the event of a positive test result. Pregnancy tests (serum and/or urine tests) should be repeated if required by local guidelines.
- h. After Cycle 1, laboratory samples can be collected up to 72 hours prior to the scheduled time point. PT/INR, CBC with differential, chemistry panel, and liver panel to be performed every cycle. Details for collection can be found in Section 7.1.3 Laboratory Procedure/Assessments. Liver panel to include albumin, ALT, AST, total bilirubin, alkaline phosphatase, direct bilirubin, and total protein.
- While on treatment, UA and thyroid function tests will be performed every other cycle.

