- In subjects who experience PD or starts a new anti-cancer therapy contact should be made (by telephone or visit) approximately O12W to assess for survival status. Updated survival status may be requested by the Sponsor at any time during the course of the study. Upon Sponsor notification, all subjects who do not/will not have a scheduled study visit or study contact during the Sponsor defined time period will be contacted for their survival status (excluding subjects that have a death event previously recorded).
- In general, the window for each visit is ± 3 days unless otherwise noted.
- SAEs will be followed through 90 days following cessation of treatment, or 30 days following cessation of treatment if the subject initiates new anticancer therapy, whichever is earlier. All protocol specified hepatic ECIs will be collected throughout the study as listed in Section 7.2.3.2. If any of the hepatic ECI criteria are met, collect the Child Pugh score with each visit until the hepatic ECIs resolve.
- Laboratory and ECOG tests for determining eligibility are to be performed within 7 days prior to the first retreatment dose of study drug. AFP will be measured every 3 weeks (21 ± 7 days) calculated from the date of randomization.
- For women of reproductive potential, a urine or serum pregnancy test should be performed within 72 hours prior to receiving the first dose of study medication (Cycle 1 Day 1). A serum test can be done if urine is not appropriate. Additionally, if urine test is positive or is not evaluable, a serum test is required. Subjects must be excluded/discontinued in the event of a positive test result. Pregnancy tests (serum and/or urine tests) should be repeated if required by local guidelines.
- f. After Cycle 1, laboratory samples can be collected up to 72 hours prior to the scheduled time point. CBC, chemistry, and liver panel to be performed every cycle. Liver panel to include albumin, ALT, AST, total bilirubin, alkaline phosphatase, direct bilirubin, and total protein.
- Urinalysis and thyroid function tests to be performed every other cycle.
- Tumor imaging should be performed within 21 days prior to starting or restarting study treatment and continue to be performed every 6 weeks (42±7 days) calculated from the first dose of retreatment, or more frequently if clinically indicated.

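### Does the 14-day limit on ECI reporting conflict with collecting hepatic ECIs for the whole study?

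*Protocol*

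**What the plan says.** Protocol Section 7.2.3.2 opens with a duty that has no end date: "Selected non-serious and serious adverse events are also known as Events of Clinical Interest (ECI) and must be reported to the Sponsor". It then sets the post-randomization window for 24-hour reporting, which runs "through 14 days following cessation of treatment, any ECI, or follow up to an ECI". Below that comes the list of what counts as an ECI. Item 2 of the list, the hepatic events, requires "notification of the event(s) to the Sponsor within 24 hours via electronic media or paper" and gives no end date.

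Section 5.2.1.3, the hepatic management guidance, repeats the requirement ("notification of the Sponsor within 24 hours"), also without an end date, and then defers: "Refer to Section 7.2.3.2 for reporting guidelines and the definition of hepatic ECIs".

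Footnote c of flow chart 6.1 reads "All protocol specific hepatic ECIs will be collected throughout the study as listed in Section 7.2.3.2". The matching footnote of flow chart 6.2 reads "All protocol specified hepatic ECIs will be collected throughout the study as listed in Section 7.2.3.2". Footnote d of 6.1 asks sites, once a hepatic ECI criterion is met, to "document the Child Pugh score with each visit until the hepatic ECIs resolve".

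**The concern.** The footnotes promise collection for the whole study but cite a section whose only dated post-treatment rule ends at 14 days. Within that section, item 2 can be read as an open-ended notification duty beside a dated one. The safety visit, which carries the last scheduled liver panel, comes at about 30 days. A non-serious transaminase or bilirubin rise found there would be outside 24-hour reporting under one sentence and inside it under another.

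Hepatic ECIs are named under the safety endpoints in Protocol Section 8.4.2 and SAP Section 3.4.2. If sites followed different passages, the recorded number could depend partly on site practice. In a liver-cancer population that would weaken a descriptive safety result that readers will look for.

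**Working it through.** No figure in the plan rests on this point, so the check sets the windows side by side and then compares dates.

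| Protocol section | Duty | Window after treatment |
|---|---|---|
| 7.2.3.2, dated sentence | 24-hour notification, any ECI | 14 days from cessation |
| 7.2.3.2 item 2; 5.2.1.3 | 24-hour notification, hepatic ECIs | none stated |
| 6.1 and 6.2, footnote c | collecting hepatic ECIs | whole study |
| 5.5.1 | recording medication for ECIs | continues past 30 days from last dose |
| 7.2 | reporting all AEs | 30 days from cessation |
| 7.1.6.3.1 | recording all AEs | up to the safety visit |
| 7.2.3.1 | 24-hour reporting, SAEs | 90 days, or 30 with new anticancer therapy |

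**Notification.** Section 7.2.3.2 belongs to Section 7.2.3, whose heading concerns immediate reporting. Its dated sentence covers every ECI. Item 2 sits beneath it in the list that defines ECIs; it repeats the 24-hour speed and sets no rival window. Its companion duty is to hold study treatment, which presupposes a subject still being dosed. Section 5.2.1.3 hands reporting back to 7.2.3.2. One dated rule therefore governs notification.

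**Collection.** The footnotes speak of collecting, not of notifying. Their pointer to 7.2.3.2 is naturally a pointer to the list of events. Section 5.5.1 expects medication to be recorded for ECIs beyond day 30, which makes sense only if ECIs are still being captured then. Flow charts 6.1 and 6.2 both mark AE review at the post-treatment follow-up visits every 6 weeks, and in 6.2 that cell carries footnote c.

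**Dates, counted from last dose.** The safety visit is at 30 ± 7 days, that is, days 23 to 37. Distance from the close of the notification window:
- earliest: 23 − 14 = 9 days
- target: 30 − 14 = 16 days
- latest: 37 − 14 = 23 days

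New anticancer therapy can bring the visit forward (Section 7.1.6.3.1).

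**Dates, counted from discontinuation.** If discontinuation falls on day D after last dose, the window closes on day D + 14. It reaches day 30 when D ≥ 30 − 14 = 16. The starting point therefore decides whether a finding at the safety visit needs 24-hour notification.

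**What is captured regardless.**
- Serious hepatic events: 24-hour SAE reporting to day 90 (30 with new therapy), and related serious events at any time under the closing paragraphs of Section 7.2.3.1.
- Non-serious events up to the safety visit: ordinary AE records, since Section 7.2 counts an unfavourable laboratory finding as a possible AE.
- Later non-serious events: the whole-study footnotes, through AE review and unscheduled tests.

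**Analysis.** OS, PFS and ORR do not use hepatic ECIs. SAP Section 3.5.2 treats safety intervals as descriptive. Protocol Table 13 and SAP Table 5 have no row named for hepatic ECIs, so no planned interval is tied to their count.

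**The case for a change.** The strongest case for a change is that the split between notification and collection has to be inferred. Item 2 says that all the listed hepatic events need 24-hour notification. The 14-day sentence also limits follow-up reports, while footnote d of 6.1 wants Child-Pugh scores until resolution. Fourteen days is the shortest post-treatment reporting window in the protocol: AEs run 30 days, SAEs 90 (30 with new therapy), and pregnancies 120 (30 with new therapy). No liver panel is scheduled after the safety visit, and AE review is not marked at survival follow-up, so whole-study collection rests on unscheduled information once a subject reaches that phase. The nearest row in SAP Table 5, immune-mediated hepatitis, is not equivalent, because Section 5.2.1.3 makes immune-related hepatitis a diagnosis of exclusion. A clarifying sentence would be cheap.

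Part of this stands. The split is unstated, and the starting point is undefined. The second gap is not peculiar to ECIs: the AE and SAE windows also run from cessation without saying which date is meant. Some sites may send an expedited report for a day-30 finding and others may not. That difference lies in how fast a non-serious event reaches the sponsor; the event is still recorded. The thin follow-up after the safety visit comes from the visit schedule, and rewording the windows would not alter it. The missing table row is a matter of extra descriptive detail: Protocol Table 13 has rows for predefined limits of change, although the documents do not say whether the hepatic thresholds count as such.

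The 6.2 header dates the safety visit from discontinuation, whereas Section 7.1.6.3.1 dates it from last dose. That is a separate labelling slip.

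**Conclusion.** No change to the plan is needed. The passages support one coherent reading: expedited notification of ECIs for 14 days after treatment, and recording of hepatic ECIs for the whole study. A sensible site or analyst would fill the gap that way.

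The residue is small: 24-hour notification of non-serious hepatic ECIs after day 14, and the completeness of non-serious ones after about day 30. Serious events and non-serious events up to the safety visit are captured under either reading, and no hypothesis, boundary or planned interval for hepatic ECIs depends on the choice.

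This rests on two assumptions. The footnotes' pointer to Section 7.2.3.2 means its list of events and not its 14-day limit. The data-entry guidelines and site binder cited there, which are not among the documents, do not instruct otherwise. How many events fall in the uncertain period cannot be worked out from the protocol or SAP. If the protocol were reopened for another reason, one sentence separating the two windows and naming their starting point would be a courtesy to sites, with no effect on the analysis.

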7.2.3.3 Protocol-Specific Exceptions to Serious Adverse Event Reporting

Efficacy endpoints as outlined in this section will not be reported to the Sponsor as described in Section 7.2.3.

Specifically, the suspected/actual events covered in this exception include any event that is disease progression of the cancer under study.

The Sponsor will monitor unblinded aggregated efficacy endpoint events and safety data to ensure the safety of the subjects in the trial. Any suspected endpoint which upon review is not progression of the cancer under study will be forwarded to global safety as a SAE within 24 hours of determination that the event is not progression of the cancer under study.

7.2.4 Evaluating Adverse Events

An investigator who is a qualified physician will evaluate all adverse events according to the NCI Common Terminology for Adverse Events (CTCAE), version 4.0. Any adverse event which changes CTCAE grade over the course of a given episode will have each change of grade recorded on the adverse event case report forms/worksheets.

All adverse events regardless of CTCAE grade must also be evaluated for seriousness.

Protocol/Amendment No.: 394-06

 Table 7
 Evaluating Adverse Events

An investigator who is a qualified physician, will evaluate all adverse events as to:

V4.0 CTCAE Grading	Grade 1	Mild; asymptomatic or mid symptoms; clinical or diagnostic observations only; intervention not indicated.				
	Grade 2	Moderate; minimal, local or noninvasive intervention indicated; limiting age-appropriate instrumental ADL.				
	Grade 3	Severe or medically significant but not immediately life-threatening; hospitalization or prolongation or hospitalization indicated;				
		disabling; limiting self-care ADL.				
	Grade 4	Life threatening consequences; urgent intervention indicated.				
	Grade 5	Death related to AE				
Seriousness	A serious advers	e event is any adverse event occurring at any dose or during any use of Sponsor's product that:				
	†Results in deat					
		ning; or places the subject, in the view of the investigator, at immediate risk of death from the event as it occurred (Note: This does not include an at, had it occurred in a more severe form, might have caused death.); or				
	†Results in a pe	rsistent or significant disability/incapacity (substantial disruption of one's ability to conduct normal life functions); or				
	hospitalization is worsened is not a patient's medica					
	†Is a congenital	anomaly/birth defect (in offspring of subject taking the product regardless of time to diagnosis);or				
	Is a new cancer requirements); o	Is a new cancer (that is not a condition of the study) (although not serious per ICH definition, is reportable to the Sponsor within 24 hours to meet certain local				
		Is an overdose (whether accidental or intentional). Any adverse event associated with an overdose is considered a serious adverse event for collection purposes. An overdose that is not associated with an adverse event is considered a non-serious event of clinical interest and must be reported within 24 hours.				
	Other important medical events that may not result in death, not be life threatening, or not require hospitalization may be considered a serious adverse event when, based upon appropriate medical judgment, the event may jeopardize the subject and may require medical or surgical intervention to prevent one of the outcomes listed previously (designated above by a †).					
Duration		and stop dates of the adverse event. If less than 1 day, indicate the appropriate length of time and units				
Action taken		event cause the Sponsor's product to be discontinued?				
Relationship to		's product cause the adverse event? The determination of the likelihood that the Sponsor's product caused the adverse event will be provided by an				
Sponsor's	investigator who	is a qualified physician. The investigator's signed/dated initials on the source document or worksheet that supports the causality noted on the AE				
Product	form, ensures that a medically qualified assessment of causality was done. This initialed document must be retained for the required regulatory time frame. The					
	criteria below are intended as reference guidelines to assist the investigator in assessing the likelihood of a relationship between the test drug and the adverse event					
	based upon the available information.					
	The following components are to be used to assess the relationship between the Sponsor's product and the AE; the greater the correlation with the components					
	and their respective elements (in number and/or intensity), the more likely the Sponsor's product caused the adverse event (AE):					
	Exposure	Is there evidence that the subject was actually exposed to the Sponsor's product such as: reliable history, acceptable compliance assessment (pill				
		count, diary, etc.), expected pharmacologic effect, or measurement of drug/metabolite in bodily specimen?				
	Time Course	Did the AE follow in a reasonable temporal sequence from administration of the Sponsor's product? Is the time of onset of the AE compatible with a drug-induced effect (applies to trials with investigational medicinal product)?				
	Likely Cause	Is the AE not reasonably explained by another etiology such as underlying disease, other drug(s)/vaccine(s), or other host or environmental factors				

Protocol/Amendment No.: 394-06

Relationship	The following c	omponents are to be used to assess the relationship between the test drug and the AE: (continued)	
to Sponsor's	Dechallenge	Was the Sponsor's product discontinued or dose/exposure/frequency reduced?	
Product	If yes, did the AE resolve or improve?		
(continued)			
		(Note: This criterion is not applicable if: (1) the AE resulted in death or permanent disability; (2) the AE resolved/improved despite continuation of	
		the Sponsor's product; or (3) the trial is a single-dose drug trial); or (4) Sponsor's product(s) is/are only used one time.)	
	Rechallenge	Was the subject re-exposed to the Sponsor's product in this study?	
		If yes, did the AE recur or worsen?	
		If yes, this is a positive rechallenge. If no, this is a negative rechallenge.	
		(Note: This criterion is not applicable if: (1) the initial AE resulted in death or permanent disability, or (2) the trial is a single-dose drug trial); or (3) Sponsor's product(s) is/are used only one time).	
		NOTE: IF A RECHALLENGE IS PLANNED FOR AN ADVERSE EVENT WHICH WAS SERIOUS AND WHICH MAY HAVE BEEN	
		CAUSED BY THE SPONSOR'S PRODUCT, OR IF REEXPOSURE TO THE SPONSOR'S PRODUCT POSES ADDITIONAL POTENTIAL	
		SIGNIFICANT RISK TO THE SUBJECT, THEN THE RECHALLENGE MUST BE APPROVED IN ADVANCE BY THE SPONSOR	
		CLINICAL DIRECTOR AS PER DOSE MODIFICATION GUIDELINES IN THE PROTOCOL.	
	Consistency	Is the clinical/pathological presentation of the AE consistent with previous knowledge regarding the Sponsor's product or drug class pharmacology	
	with Trial	or toxicology?	
	Treatment		
	Profile		
The assessment of consideration of the		e reported on the case report forms /worksheets by an investigator who is a qualified physician according to his/her best clinical judgment, including	
Record one of the	e following	Use the following scale of criteria as guidance (not all criteria must be present to be indicative of a Sponsor's product relationship).	
Yes, there is a respossibility of Sporelationship.		There is evidence of exposure to the Sponsor's product. The temporal sequence of the AE onset relative to the administration of the Sponsor's product is reasonable. The AE is more likely explained by the Sponsor's product than by another cause.	
No, there is not a possibility of Spo relationship		Subject did not receive the Sponsor's product OR temporal sequence of the AE onset relative to administration of the Sponsor's product is not reasonable OR the AE is more likely explained by another cause than the Sponsor's product. (Also entered for a subject with overdose without an associated AE.)	

Protocol/Amendment No.: 394-06

